6.2. Assessing and Recording Adverse Events

An adverse event is defined as any untoward medical occurrence in a patient or clinical investigation subject administered a pharmaceutical product and which does not necessarily have to have a causal relationship with this treatment. An adverse event can therefore be any unfavorable and unintended sign (including an abnormal laboratory finding, for example), symptom, or disease temporally associated with the use of a medicinal product or protocol-specified procedure, whether or not considered related to the medicinal product or protocol-

specified procedure. Any worsening (i.e., any clinically significant adverse change in frequency and/or intensity) of a preexisting condition that is temporally associated with the use of the Merck's product, is also an adverse event.

Changes resulting from normal growth and development that do not vary significantly in frequency or severity from expected levels are not to be considered adverse events. Examples of this may include, but are not limited to, teething, typical crying in infants and children and onset of menses or menopause occurring at a physiologically appropriate time.

Merck product includes any pharmaceutical product, biological product, device, diagnostic agent or protocol-specified procedure, whether investigational (including placebo or active comparator medication) or marketed, manufactured by, licensed by, provided by or distributed by Merck for human use.

Adverse events may occur during the course of the use of Merck product in clinical trials, or as prescribed in clinical practice, from overdose (whether accidental or intentional), from abuse and from withdrawal.

Progression of the cancer under study is not considered an adverse event.

All adverse events that occur after the consent form is signed but before treatment allocation/registration must be reported by the investigator if they cause the subject to be excluded from the trial, or are the result of a protocol-specified intervention, including but not limited to washout or discontinuation of usual therapy, diet, placebo treatment or a procedure.

From the time of treatment allocation through 30 days following cessation of treatment, the investigator must report all adverse events. Such events will be recorded at each examination on the Adverse Event case report forms/worksheets. The reporting timeframe for adverse events meeting any serious criteria is described in section 7.2.3.1. The investigator will make every attempt to follow all subjects with non-serious adverse events for outcome.

Adverse events will not be collected for subjects during the pre-screening period (for determination of archival tissue status) as long as that subject has not undergone any protocol-specified procedure or intervention. If the subject requires a blood draw, fresh tumor biopsy etc., the subject is first required to provide consent to the main study and AEs will be captured according to guidelines for standard AE reporting.

6.2.1 Definition of an Overdose for This Protocol and Reporting of Overdose to the Sponsor and to Merck

For purposes of this trial, an overdose of pembrolizumab will be defined as any dose of 1,000 mg or greater (\geq 5 times the indicated dose). No specific information is available on the treatment of overdose of pembrolizumab. Appropriate supportive treatment should be provided if clinically indicated. In the event of overdose, the subject should be observed closely for signs of toxicity. Appropriate supportive treatment should be provided if clinically indicated.

If an adverse event(s) is associated with ("results from") the overdose of a Merck product, the adverse event(s) is reported as a serious adverse event, even if no other seriousness criteria are met.

If a dose of Merck's product meeting the protocol definition of overdose is taken without any associated clinical symptoms or abnormal laboratory results, the overdose is reported as a non-serious Event of Clinical Interest (ECI), using the terminology "accidental or intentional overdose without adverse effect."

All reports of overdose with and without an adverse event must be reported within 24 hours to the Sponsor and within 2 working days hours to Merck Global Safety. (Attn: Worldwide Product Safety; [contact])

6.2.2 Reporting of Pregnancy and Lactation to the Sponsor and to Merck

Although pregnancy and lactation are not considered adverse events, it is the responsibility of investigators or their designees to report any pregnancy or lactation in a subject (spontaneously reported to them) that occurs during the trial.

Pregnancies and lactations that occur after the consent form is signed but before treatment allocation/registration must be reported by the investigator if they cause the subject to be excluded from the trial, or are the result of a protocol-specified intervention, including but not limited to washout or discontinuation of usual therapy, diet, placebo treatment or a procedure.

Pregnancies and lactations that occur from the time of treatment allocation/registration through 120 days following cessation of Sponsor's product, or 30 days following cessation of treatment if the subject initiates new anticancer therapy, whichever is earlier, must be reported by the investigator. All reported pregnancies must be followed to the completion/termination of the pregnancy. Pregnancy outcomes of spontaneous abortion, missed abortion, benign hydatidiform mole, blighted ovum, fetal death, intrauterine death, miscarriage and stillbirth must be reported as serious events (Important Medical Events). If the pregnancy continues to term, the outcome (health of infant) must also be reported.

Such events must be reported within 24 hours to the Sponsor and within 2 working days to Merck Global Safety. (Attn: Worldwide Product Safety; [contact])

6.2.3 Immediate Reporting of Adverse Events to the Sponsor and to Merck

6.2.3.1 Serious Adverse Events

A serious adverse event is any adverse event occurring at any dose or during any use of Merck's product that:

- Results in death;
- Is life threatening;
- Results in persistent or significant disability/incapacity;
- Results in or prolongs an existing inpatient hospitalization;
- Is a congenital anomaly/birth defect;
- Is another important medical event

- Note: In addition to the above criteria, adverse events meeting either of the below criteria, although not serious per ICH definition, are reportable to the Merck in the same timeframe as SAEs to meet certain local requirements. Therefore, these events are considered serious by Merck for collection purposes.
 - Is a new cancer (that is not a condition of the study);
 - Is associated with an overdose.

Refer to Table 11 for additional details regarding each of the above criteria.

For the time period beginning when the consent form is signed until treatment allocation/registration, any serious adverse event, or follow up to a serious adverse event, including death due to any cause other than progression of the cancer under study that occurs to any subject must be reported within 24 hours to the Sponsor and within 2 working days to Merck Global Safety if it causes the subject to be excluded from the trial, or is the result of a protocol-specified intervention, including but not limited to washout or discontinuation of usual therapy, diet, placebo treatment or a procedure.

For the time period beginning at treatment allocation/registration through 90 days following cessation of treatment, or 30 days following cessation of treatment if the subject initiates new anticancer therapy, whichever is earlier, any serious adverse event, or follow up to a serious adverse event, including death due to any cause other than progression of the cancer under study (reference Table 11 for additional details), whether or not related to the Merck product, must be reported within 24 hours to the Sponsor and within 2 working days to Merck Global Safety.

Additionally, any serious adverse event, considered by an investigator who is a qualified physician to be related to Merck product that is brought to the attention of the investigator at any time following consent through the end of the specified safety follow-up period specified in the paragraph above, or at any time outside of the time period specified in the previous paragraph also must be reported immediately to the Sponsor and to Merck Global Safety.

All subjects with serious adverse events must be followed up for outcome.

SAE reports and any other relevant safety information are to be forwarded to the Merck Global Safety [contact]

A copy of all 15 Day Reports and Annual Progress Reports is submitted as required by FDA, European Union (EU), Pharmaceutical and Medical Devices agency (PMDA) or other local regulators. Investigators will cross reference this submission according to local regulations to the Merck Investigational Compound Number (IND, CSA, etc.) at the time of submission. Additionally investigators will submit a copy of these reports to Merck & Co., Inc. (Attn: Worldwide Product Safety; [contact]) at the time of submission to FDA.

6.2.4 Events of Clinical Interest

Selected non-serious and serious adverse events are also known as Events of Clinical Interest (ECI) and must be reported within 24 hours to the Sponsor and within 2 working days to Merck Global Safety. (Attn: Worldwide Product Safety; [contact]).

For the time period beginning when the consent form is signed until treatment allocation/registration, any ECI, or follow up to an ECI, that occurs to any subject must be reported within 24 hours to the Sponsor and within 2 working days to Merck Global Safety if it causes the subject to be excluded from the trial, or is the result of a protocol-specified intervention, including but not limited to washout or discontinuation of usual therapy, diet, placebo treatment or a procedure.

For the time period beginning at treatment allocation through 90 days following cessation of treatment, or 30 days following cessation of treatment if the subject initiates new anticancer therapy, whichever is earlier, any ECI, or follow up to an ECI, whether or not related to Merck product, must be reported within 24 hours to the Sponsor and within 24 hours to Merck Global Safety.

Events of clinical interest for this trial include:

- 1. An overdose of Merck product, as defined in Section 6.2.1 Definition of an Overdose for This Protocol and Reporting of Overdose to the Sponsor, that is not associated with clinical symptoms or abnormal laboratory results.
- 2. An elevated AST or ALT lab value that is greater than or equal to 3X the upper limit of normal and an elevated total bilirubin lab value that is greater than or equal to 2X the upper limit of normal and, at the same time, an alkaline phosphatase lab value that is less than 2X the upper limit of normal, as determined by way of protocol-specified laboratory testing or unscheduled laboratory testing.*

*Note: These criteria are based upon available regulatory guidance documents. The purpose of the criteria is to specify a threshold of abnormal hepatic tests that may require an additional evaluation for an underlying etiology.

6.2.5 Protocol-Specific Exceptions to Serious Adverse Event Reporting

Efficacy endpoints as outlined in this section will not be reported to Merck as described in Section 6.2.3- Immediate Reporting of Adverse Events to the Sponsor and to Merck, unless there is evidence suggesting a causal relationship between the drug and the event. Any such event will be submitted to the Sponsor within 24 hours and to Merck Global Safety within 2 working days either by electronic or paper media.

Specifically, the suspected/actual events covered in this exception include any event that is disease progression of the cancer under study.

The Sponsor will monitor unblinded aggregated efficacy endpoint events and safety data to ensure the safety of the subjects in the trial. Any suspected endpoint which upon review is not progression of the cancer under study will be forwarded to Merck Global Safety as a SAE

within 2 working days of determination that the event is not progression of the cancer under study

Hospitalization related to convenience (e.g. transportation issues etc.) will not be considered a SAE.

6.2.6 Evaluating Adverse Events

An investigator who is a qualified physician will evaluate all adverse events according to the NCI Common Terminology for Adverse Events (CTCAE), version 4.0. Any adverse event which changes CTCAE grade over the course of a given episode will have each change of grade recorded on the adverse event case report forms/worksheets.

All adverse events regardless of CTCAE grade must also be evaluated for seriousness.

Table 11. Evaluating Adverse Events

An investigator who is a qualified physician, will evaluate all adverse events as to:

V4.0 CTCAE Grading	Grade 1	Mild; asymptomatic or mid symptoms; clinical or diagnostic observations only; intervention not indicated.			
	Grade 2	Moderate; minimal, local or noninvasive intervention indicated; limiting age-appropriate instrumental ADL.			
	Grade 3	Severe or medically significant but not immediately life-threatening; hospitalization or prolongation or hospitalization indicated; disabling; limiting self-care ADL.			
	Grade 4	Life threatening consequences; urgent intervention indicated.			
	Grade 5	Death related to AE			
Seriousness	A serious adv	verse event is any adverse event occurring at any dose or during any use of Merck product that:			
	†Results in d	leath; or			
	†Is life threatening; or places the subject, in the view of the investigator, at immediate risk of death from the event as it occurred (Note: This does not include an adverse event that, had it occurred in a more severe form, might have caused death.); or				
	†Results in a persistent or significant disability/incapacity (substantial disruption of one's ability to conduct normal life functions); or				
	†Results in or prolongs an existing inpatient hospitalization (hospitalization is defined as an inpatient admission, regardless of length of stay, even if the hospitalization is a precautionary measure for continued observation. (Note: Hospitalization for an elective procedure to treat a pre-existing condition that has not worsened is not a serious adverse event. A pre-existing condition is a clinical condition that is diagnosed prior to the use of a Merck product and is documented in the patient's medical history.); or				
	†Is a congen	ital anomaly/birth defect (in offspring of subject taking the product regardless of time to diagnosis);or			
		cer (that is not a condition of the study) (although not serious per ICH definition, is reportable to the Sponsor within 24 hours and to Merck within 2 to meet certain local requirements); or			
	Is an overdose (whether accidental or intentional). Any adverse event associated with an overdose is considered a serious adverse event for collection purposes. An overdose that is not associated with an adverse event is considered a non-serious event of clinical interest and must be reported within 24 hours to the Sponsor and to Merck within 2 working days.				
	based upon ap	tant medical events that may not result in death, not be life threatening, or not require hospitalization may be considered a serious adverse event when, peropriate medical judgment, the event may jeopardize the subject and may require medical or surgical intervention to prevent one of the outcomes listed esignated above by a †).			

Duration	Record the start	and stop dates of the adverse event. If less than 1 day, indicate the appropriate length of time and units
Action taken	Did the adverse	event cause Merck product to be discontinued?
Relationship to Merck Product	Did Merck product cause the adverse event? The determination of the likelihood that Merck product caused the adverse event will be provided by an investigator who is a qualified physician. The investigator's signed/dated initials on the source document or worksheet that supports the causality noted on the AE form, ensures that a medically qualified assessment of causality was done. This initialed document must be retained for the required regulatory time frame. The criteria below are intended as reference guidelines to assist the investigator in assessing the likelihood of a relationship between the test drug and the adverse event based upon the available information. The following components are to be used to assess the relationship between Merck product and the AE; the greater the correlation with the components and their respective elements (in number and/or intensity), the more likely Merck product caused the adverse event (AE):	
	Exposure Time Course Likely Cause	Is there evidence that the subject was actually exposed to Merck product such as: reliable history, acceptable compliance assessment (pill count, diary, etc.), expected pharmacologic effect, or measurement of drug/metabolite in bodily specimen? Did the AE follow in a reasonable temporal sequence from administration of Merck product? Is the time of onset of the AE compatible with a drug-induced effect (applies to trials with investigational medicinal product)? Is the AE not reasonably explained by another etiology such as underlying disease, other drug(s)/vaccine(s), or other host or environmental factors

Relationship	The following components are to be used to assess the relationship between the test drug and the AE: (continued)		
to Merck Product	Dechallenge Was Merck product discontinued or dose/exposure/frequency reduced?		
(aantinuad)		If yes, did the AE resolve or improve?	
(continued)		If yes, this is a positive dechallenge. If no, this is a negative dechallenge.	
		(Note: This criterion is not applicable if: (1) the AE resulted in death or permanent disability; (2) the AE resolved/improved despite continuation of the Sponsor's product; or (3) the trial is a single-dose drug trial); or (4) Sponsor's product(s) is/are only used one time.)	
	Rechallenge	Was the subject re-exposed to Merck product in this study?	
		If yes, did the AE recur or worsen?	
		If yes, this is a positive rechallenge. If no, this is a negative rechallenge.	
		(Note: This criterion is not applicable if: (1) the initial AE resulted in death or permanent disability, or (2) the trial is a single-dose drug trial); or (3) Sponsor's product(s) is/are used only one time).	
		NOTE: IF A RECHALLENGE IS PLANNED FOR AN ADVERSE EVENT WHICH WAS SERIOUS AND WHICH MAY HAVE BEEN CAUSED BY MERCK PRODUCT, OR IF REEXPOSURE TO MERCK PRODUCT POSES ADDITIONAL POTENTIAL SIGNIFICANT RISK TO THE SUBJECT, THEN THE RECHALLENGE MUST BE APPROVED IN ADVANCE BY THE SPONSOR AS PER DOSE MODIFICATION GUIDELINES IN THE PROTOCOL.	
	Consistency with Trial Treatment Profile	Is the clinical/pathological presentation of the AE consistent with previous knowledge regarding Merck product or drug class pharmacology or toxicology?	
	of relationship will the above elements	be reported on the case report forms /worksheets by an investigator who is a qualified physician according to his/her best clinical judgment, including s.	
Record one of th	ne following	Use the following scale of criteria as guidance (not all criteria must be present to be indicative of Merck product relationship).	
Yes, there is a repossibility of Merelationship.		There is evidence of exposure to Merck product. The temporal sequence of the AE onset relative to the administration of Merck product is reasonable. The AE is more likely explained by Merck product than by another cause.	
		Subject did not receive the Merck product OR temporal sequence of the AE onset relative to administration of Merck product is not reasonable OR the AE is more likely explained by another cause than the Merck product. (Also entered for a subject with overdose without an associated AE.)	

6.2.7 Sponsor Responsibility for Reporting Adverse Events

All Adverse Events will be reported to regulatory authorities, IRB/IECs and investigators in accordance with all applicable global laws and regulations.

7. STATISTICAL ANALYSIS PLAN

7.1. Statistical Analysis Plan Summary

Key elements of the statistical plan are summarized in Table 12 below. A comprehensive plan is detailed in section 7.2

Table 12: Statistical Overview

Study Design Overview	Open-label, single arm phase II study of pembrolizumab in patients with advanced solid tumors with leptomeningeal carcinomatosis (LMD)
Treatment Assignment	pembrolizumab 200mg Q3W
Analysis Population	Eligible patients who receive at least one dose of pembrolizumab
Primary Endpoint	CNS response at 12 weeks based on either radiologic, cytologic or clinical evidence
Statistical Methods for Key Efficacy Analyses	The proportion of CNS response and associated 95% exact confidence interval will be provided
Statistical Methods for	Descriptive analysis based on Clopper-Pearson's exact binomial confidence interval method.
Key Safety Analyses	
Multiplicity	N.A.
Sample Size and Power	No formal statistical inference will be provided. The proposed sample size will provide appropriate estimation precision for the primary efficacy endpoint.

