4.1.5.2.5 Tumor Tissue Analyses

Archival tissue, pre-treatment biopsy tissue or on-treatment biopsy tissue will be analyzed in patients where this tissue is available. From a genomic perspective, analyses from available tumor cells may include but may not be limited to: next generation sequencing of tumor and matched normal tissue, this will define the genomic landscape of these tumor cells. Candidate neoantigen determination using a bioinformatics platform. From an immunologic perspective, analyses from available tumor cells may include but may not be limited to by immunohistochemistry using monoclonal antibodies for immune checkpoint ligands and TIL populations, immune ligand expression of TILs using multi-color flow cytometry, assessment of soluble immune factors in the tumor microenvironment, and assessment for the presence of antigen-specific T-cells using MHC-multimer assays. Analyses will be prioritized depending on the amount of tissue available for analysis.

Table 2: Biomarker Analysis Table

	Pre-Tx	C1D1	C2D1	C3D1	C4D1	Post-4	Co-Investigators/					
						cycles	Site of Testing					
Pembrolizumab		X	X	X	X							
	Biospecimen collection for analysis											
CSF X X X												
PBMCs/Serum	X			X		X						
Tumor tissue*	X*											
Γ	Cumor correl	ates (seru	ım +/- tum	or tissue*	if availabl	e)						
Cell-free DNA	X			X		X	[name]/					
							[name] Lab					
Immune activation*	X*						[name] Lab					
	T-cell corre	lates (PB)	Ls +/- tum	or TILs* i	f available	·)						
Immune activation in PBLs	X			X		X	[name] Lab					
Immune activation in	X*						[name] Lab					
TILs*												
	CSF analysis	(tumor c	ells, CSF-	tDNA, in	mune cell	s)						
CSF tumor cells	X			X		X	[name]/					
							[name] Lab					
CSF- tDNA	X			X		X	[name]/					
							[name] Lab					
CSF immune correlates	X		-	X		X	[name] Lab					

METHODOLOGY

- 4.2 Patient Sample
- **4.2.1** Sample Size: The accrual objective for this study is 18 eligible and evaluable patients
- **4.2.2 Accrual Rate**: The expected accrual rate for this study is approximately 1 patient per month
- **4.2.3 Gender:** Male and Female subjects
- **4.2.4** Race: Minorities will be actively recruited.
- **4.2.5 Diagnosis/Condition for Entry into the Trial:** Patients with advanced solid tumors

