7.2. Statistical Analysis Plan

7.2.1 Statistical Plan

This is an open-label phase II study aimed at establishing the efficacy of single agent pembrolizumab, at the FDA-approved dose of 200mg every 3 weeks, in patients with solid

tumors and LMD. The primary endpoint will be CNS response at 12 weeks/after 4 cycles of therapy. The sample size is calculated with Clopper-Pearson's exact binomial confidence interval method. With 16 analyzable patients, defined as eligible patients who receive at least one dose of pembrolizumab, we determine that we will have an appropriate level of estimation accuracy for the first study of this experimental regimen. The following table summarizes the two-sided 90% exact confidence interval for different observed CNS response rate. Guarding against a 10% rate of patients either being ineligible or dropping out, the final sample size is 18 patients. If a higher rate of ineligible and drop-out rate is observed during the study conduct, the protocol may be amended to ensure at least 16 analyzable cases.

No. of patients with CNS response (%)	90% Confidence Interval for Observed CNS Response Rate (N=16)	
	Lower (%)	Upper (%)
1 (6.3%)	0.3	26.4
2 (12.5%)	2.3	34.4
3 (18.8%)	5.3	41.7
4 (25%)	9.0	48.4
5 (31.3%)	13.2	54.8
6 (37.5%)	17.8	60.1

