7.2.4 Primary Efficacy Endpoint

CNS response

CNS response rate is defined as the proportion of the subjects in the analysis population who have a radiologic reduction in size of measurable CNS tumor lesions on an MRI brain scan, develop clearance of positive CSF cytology on 2 consecutive CSF specimens after an initial positive specimen has been obtained, or an improvement in neurologic function, as detailed in Table 8. In patients with more than one available response criterion, the most easily assessable criterion will be used.

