7.2.5. Secondary Efficacy Endpoints

1. CNS Progression-Free Survival (PFS)

PFS is defined as the time from first day of study treatment until date of progression. Progression will be stratified into CNS progression (radiologic or cytology or clinical). CNS radiologic progression will be assessed by MRI criteria, CNS cytologic progression will be determined pathologically, and neurologic progression will be determined as per section 6.1.2.7 and Table 8 respectively. PFS will be calculated using the Kaplan-Meier method.

2. Overall Survival

Overall survival will be defined as the date of study entry until date of death from any cause. Cause of death will be recorded.

3. Safety

The primary safety objective of this trial is to characterize the safety and tolerability of pembrolizumab in subjects with LMD. The primary safety analysis will be based on subjects who experienced toxicities as defined by CTCAE, Version 4.0 criteria (Appendix 2). The attribution to drug, time-of-onset, duration of the event, its resolution, and any concomitant

medications administered will be recorded. AEs will be analyzed including but not limited to all AEs, SAEs, fatal AEs, and laboratory changes. Furthermore, specific immune-related adverse events (irAEs) will be collected and designated as immune-related events of clinical interest (ECIs) as described in Section 6.2.3.2

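### No safety population is defined, so a dosed patient later ruled ineligible would be absent from the analysed safety proportions

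*Combined protocol and SAP*

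**What the plan says.** Table 12 (section 7.1) has a single row for the analysis population: "Eligible patients who receive at least one dose of pembrolizumab". It stands above both the efficacy and the safety method rows. Section 7.2.1 repeats the definition when it sizes the trial: "With 16 analyzable patients, defined as eligible patients who receive at least one dose of pembrolizumab". Section 7.2.4 then uses it as the denominator of the primary endpoint: "CNS response rate is defined as the proportion of the subjects in the analysis population".

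For safety, Table 12 names Clopper-Pearson exact binomial intervals. Section 7.2.5 says only this about who is analysed: "The primary safety analysis will be based on subjects who experienced toxicities as defined by CTCAE, Version 4.0 criteria". Neither the protocol nor the SAP defines an all-treated or safety set.

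On numbers, section 7.2.1 states: "Guarding against a 10% rate of patients either being ineligible or dropping out, the final sample size is 18 patients". If losses run higher, "the protocol may be amended to ensure at least 16 analyzable cases". Section 4.2.1 says something different: "The accrual objective for this study is 18 eligible and evaluable patients".

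**The concern.** Eligibility is a reasonable condition for an efficacy set. For safety, what counts is exposure, and a patient who received the drug was exposed whether or not an entry criterion was later found unmet. A binomial interval needs a denominator. The only one the plan defines is restricted to eligible patients, because the phrase in section 7.2.5 describes patients who had events. A statistician following the text would therefore leave a dosed but ineligible patient out of both the numerator and the denominator of each toxicity proportion.

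Safety is a named secondary objective, and section 7.2.1 calls this the first study of the regimen. With 16 to 18 patients, an uncommon event may occur once or twice, so one or two omitted patients can decide whether it appears in the safety table.

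The response rate has the same restriction, stated openly. There the issue is only that the reader would not see the rate among everyone treated.

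**Working it through.** **1. The plan's own figures.** The inputs are 16 analyzable patients and a 10% allowance (section 7.2.1). 16 / (1 − 0.10) = 17.8, rounded up to 18, which agrees with the plan. The plan's 90% interval for 4/16, 9.0 to 48.4%, is also reproduced.

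**2. How many patients could be affected.** 18 − 16 = 2. The allowance combines ineligibility and drop-out, and the documents do not say how many of the two would be dosed and then ruled ineligible. A patient who drops out after one dose still meets the definition of analyzable. The range on the plan's own allowance is therefore 0 to 2 of 18. A higher loss is possible but would lead to the amendment foreseen in section 7.2.1.

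**3. Safety illustration.** The documents give no toxicity rate, so these scenarios are assumed. Table 12 gives no confidence level for safety; 95% is used here because the table uses it for response. Limits are Clopper-Pearson.

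| Scenario | Eligible and treated | All treated |
|---|---|---|
| Two excluded, toxicity only in those two | 0/16 = 0% (0 to 20.6%) | 2/18 = 11.1% (1.4 to 34.7%) |
| Two excluded, one of three toxicities among them | 2/16 = 12.5% (1.6 to 38.3%) | 3/18 = 16.7% (3.6 to 41.4%) |
| Two excluded, none of three toxicities among them | 3/16 = 18.8% (4.0 to 45.6%) | 3/18 = 16.7% (3.6 to 41.4%) |

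For 0/16 the upper limit is 1 − 0.025^(1/16) = 20.6%. The last row shows that the proportion can also rise when patients are left out.

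The chance that at least one of two excluded patients has a given toxicity is 1 − (1 − p)². For true rates p of 5%, 10%, 20% and 30% this is 10%, 19%, 36% and 51%.

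**4. Response illustration.** Suppose two treated patients are excluded, both non-responders, and four of the others respond. The eligible-only rate is 4/16 = 25.0% (95% CI 7.3 to 52.4%). The all-treated rate is 4/18 = 22.2% (6.4 to 47.6%). The difference is 2.8 percentage points.

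**5. The accrual target.** Section 7.2.1 enrols 18 to obtain 16. Section 4.2.1 asks for 18 who are eligible and evaluable, and does not define evaluable. The trial summary (section 1.0) gives 18 subjects in total, and section 4.9.2 does not replace patients who discontinue. If 18 are enrolled and one is ineligible, 17 remain and the section 4.2.1 target is missed. Reaching 18 under the same 10% allowance would need 18 / 0.9 = 20 enrolled. The two sections cannot both describe the stopping point for enrolment.

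**The case against.** The strongest reply is that the plan never says safety is restricted to eligible patients. Sections 7.2.1 and 7.2.4 tie the population to the response endpoint. Section 7.2.5 does not use the term for safety and can be read as covering any subject with a toxicity. Section 4.1.5.1.2 measures safety as a number of toxicities, which is a count. Table 12 is a summary that defers to section 7.2. This stands in part: the exclusion is implied, because no other set exists, and is not express. It does not supply the denominator that the planned exact intervals need.

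A reader might infer more than the documents support, in four ways.

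- **That safety data would be lost.** They would not. Section 6.2 requires all adverse events to be reported from treatment allocation to 30 days after treatment. Section 6.2.3.1 requires serious events for 90 days, or 30 if new anticancer therapy starts. Neither is limited to eligible patients. The gap is confined to the analysed proportions.
- **That non-responders could be dropped after the fact to raise the response rate.** The documents describe no step for re-judging eligibility once response is known. Eligibility is checked before enrolment by a tumor board (4.2.8), and against the entry criteria by the investigator or a designee (6.1.1.3). Section 4.9 does allow withdrawal where enrolment proves inappropriate, so a late finding is possible, but nothing links it to outcome.
- **That an excluded patient is likely.** Applying the whole 10% to dosed but ineligible patients gives 1 − 0.90^18 = 85% for at least one among 18. That allowance also covers drop-out, and the documents give no rate for this subgroup. At assumed rates of 1% and 2% the same formula gives 16.5% and 30.5%.
- **That the efficacy set is an error.** An eligible-and-treated set is prespecified and consistently stated. Whether it or the all-treated set is primary is a matter of choice.

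**Conclusion.** The gap is real and small. The plan defines one analysis population, limited to eligible treated patients, and gives safety no denominator of its own. Read as written, 0 to 2 of 18 patients could be missing from the safety proportions. At the upper end, a toxicity confined to two such patients would be reported as none in 16. The response rate would move by a few percentage points at most in the case worked, within wide intervals and with no formal inference planned.

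This rests on two assumptions: that the Table 12 population governs safety because no other set exists, and that at least one patient is dosed and then ruled ineligible. The documents do not say how likely the second is, and review before enrolment should keep it uncommon. The mismatch between sections 4.2.1 and 7.2.1 needs neither assumption.

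**What to change.** - In Table 12 and section 7.2.5, define the safety population as all patients who receive any pembrolizumab, regardless of eligibility, and use it as the denominator for every toxicity proportion. State the confidence level.
- Keep the eligible-and-treated set for the primary response rate if preferred, label it, and report the all-treated rate beside it. State which set serves CNS-PFS and OS, since section 7.2.5 names none.
- Restate section 4.2.1 to agree with section 7.2.1: 18 enrolled to give at least 16 analyzable.

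The cost is a few sentences and one extra table. The response rate may be slightly lower in the all-treated set. Sample size, data collection and visits do not change.
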